APPENDIX E: ASSESSMENT TOOL FOR OBSERVER

Validate an Easy to Administer Algorithm to Define Penicillin (B-lactam) Allergy Status in STD Outpatients

DMID Protocol Number (#18-0023)

PARTICIPANT I.D. _____

Assessment Tool for Observer

1. Screening Procedure (Check all that apply)

- Staff approach subjects in waiting area _____
- Flyers posted in waiting area _____
- Recruitment materials provided at reception _____
- Referral from Clinicians _____
- Allergy identified in Medical Record _____
- Other _____

2. Informed Consent Obtained (ICF) _____

3. Copy of ICF provided to participant _____

4. Questionnaire Administered _____

5. Defined as Low-Risk or High-Risk Group _____

- a. If High-Risk Defined STOP
- b. If Low-Risk Continue

6. Exclusion Criteria Assessed _____

- a. If Excluded STOP

7. SKIN TESTING GROUP

- a. Verify skin test reagents correctly labeled _____
- b. Skin Prick Targets Marked appropriately _____
- c. Skin Pricks administered in the correctly labeled area _____
- d. Positive and Negative Controls Correct _____
- e. Intradermal Targets Mapped and Marked _____
- f. Intradermal Tests administered _____
- g. Waiting Time Appropriate _____
- h. Positive and Negative Controls Correct _____
- i. If positive, photograph and document _____

8. Oral Challenge (After Skin Testing)

- a. Physical assessment and Vital Signs time =0
(Peak Flow: Use highest value of 3 successive readings) _____
- b. Oral Challenge administered _____
- c. Physical assessment and Vital Signs time =60 min. _____
- d. Results Explained to Subject _____

**Validate an Easy to Administer Algorithm to Define Penicillin (B-lactam) Allergy Status in STD
Outpatients**

DMID Protocol Number (#18-0023)

PARTICIPANT I.D. _____

9. Direct Oral Challenge

Low Dose (25 mg)

- a. Physical assessment and Vital Signs time =0 _____
- b. Oral Challenge administered _____
- c. Physical assessment and Vital Signs time =30 min. _____
- d. Results Explained to Subject _____

Full Dose (250 mg)

- a. Physical assessment and Vital Signs time =0 _____
- b. Oral Challenge administered _____
- c. Physical assessment and Vital Signs time =30 min. _____
- d. Results Explained to Subject _____

10. Participant Accessibility Survey _____

11. Notification Letter Provided _____

12. Is Action Plan Required?

Yes

No

Comments: _____

Completed By: _____ **Date:** _____
(Name, Observer Signature)

Reviewed By: _____ **Date:** _____
(Name, Site Investigator Signature)

1. INTRODUCTION

This is a multicenter clinical study to screen and enroll eligible individuals coming for care at ambulatory STD clinics and similar venues who self-report a history of PCN or other beta-lactam antibiotic allergy. The study will screen approximately 5,000 men and women to achieve 1,000 evaluable participants from 5 study sites in different geographic areas of the US over a 14-16-month recruitment period.

Two methods of validating PCN allergy will be used:

- **Method 1 – PCN Skin Test (PST) Group:** skin testing of subjects with low-risk history followed by one-step oral challenge of subjects with negative skin tests.
- **Method 2 – Direct Oral Challenge (DOC) Group:** direct two-step oral challenge of subjects with low-risk history.

Each site will perform both allergy validation interventions, Method 1 PST Group and Method 2 DOC Group. The anticipated enrollment at each site will be approximately 200 subjects overall with 100 in each group. Since each intervention has different logistical considerations, sites will enroll subjects in sequential block groups of 25. Sites will be assigned the order of block groups randomly. Each site will plan to enroll 8 block groups, 4 in each allergy validation intervention.

The analysis plan provides additional details regarding the planned statistical analysis of the study protocol (version 2.0, 09March2020). Tables, figures and listings shells will be developed prior to the start of data cleaning and included as an appendix to a future version of the plan.

2. STUDY OBJECTIVES

The study objectives described in the protocol are as follows:

2.1 Primary Objective

- Validate an algorithm which incorporates a PCN (B-lactam) allergy history screening questionnaire followed by an allergy validation intervention — 1) skin testing and oral challenge or 2) direct two-step oral challenge — to produce a short standardized post-study questionnaire (4-6 questions) for use in ambulatory STD settings.
- Determine how many subjects who report PCN (B-lactam) allergy can be treated with PCN or B-lactam drugs.

2.2 Secondary Objectives

- Assess subject and provider acceptability of a PCN (B-lactam) allergy testing algorithm.

- Determine the feasibility of implementing PCN skin testing followed by oral challenge for those with negative skin test results, or direct two-step oral challenge in an ambulatory STD setting.

3. STUDY OUTCOME MEASURES

3.1 Primary Outcome Measures

- Algorithm / PCN (B-lactam) allergy history screening questionnaire performance in ambulatory STD populations, specifically the negative predictive value (NPV) of the algorithm on true PCN (B-lactam) allergy.
- In ambulatory STD patients who report a history of PCN (B lactam) allergy and who have low-risk histories, determine the prevalence of PCN reactivity validated either by skin test or by direct oral challenge.

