6.1.2.2 Procedures After Defining Risk Category

Subjects classified with a low-risk history will progress to either skin testing (PST Group) or direct oral challenge (DOC Group), depending on which method of validating PCN allergy they are assigned. Subjects who meet the higher-risk classification will be advised that further elucidation of their allergy status will require a formal allergy evaluation. Referral resources will be provided.

All participants classified as low-risk and who meet additional qualification criteria to receive allergy testing (See Sec 6.1.3) will undergo the following procedures:

ASSIGNED TO PST GROUP

- Administration of skin test (prick test first and, if indicated, intradermal test)
- If skin test results are negative, option to receive oral challenge of 250 mg of amoxicillin
- Pre-oral challenge brief PE, assessment of vital signs and measurement of peak flow
- Administration of oral challenge
- Post-oral challenge brief PE, vital sign assessment and peak flow measurement

ASSIGNED TO DOC GROUP

- Pre-oral challenge brief PE, assessment of vital signs and measurement of peak flow
- Administration of oral challenge (first step) of 25 mg of amoxicillin, vital sign assessment and, if indicated, administration of oral challenge (second step) of 250 mg of amoxicillin
- Post-oral challenge brief PE, vital sign assessment and peak flow measurement

All participants will undergo the following procedures after allergy validation methods are offered or completed:

- Administration of subject acceptability survey on PCN testing procedures for all subjects who were offered skin testing (with or without oral challenge) or direct oral challenge
- Written documentation of PCN allergy testing results for all subjects who received skin testing (with or without oral challenge) or direct oral challenge to share with subject's medical care providers

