6.2 PCN Skin Testing

Depending on the outcome of the PCN (B-lactam) allergy history screening questionnaire, participants may qualify to receive the PCN skin test.

- Participants with a higher risk of PCN allergy will not proceed to the PCN skin test or oral challenge. Their study participation will be complete. Subjects will be provided with a written referral to local allergy providers.
- Participants with a low risk of PCN allergy and assigned to the PST intervention group will be offered the PCN skin test.

Staff will verify that qualified participants do not meet any additional criteria that would preclude them from skin testing using the Skin Test Qualification Checklist. Study staff will explain the skin testing procedures to participants who may decide to accept or decline skin testing. If they decline, they will be asked to complete the subject acceptability survey and their study participation will be complete. Staff will note the reason(s) they declined to be skin tested on the appropriate CRF.

Study staff will perform the allergy skin testing for PCN allergy in accordance with standard allergy testing procedures and instructions provided in the PRE-PEN® kit package insert.³¹ Prick (Puncture) tests will be performed before proceeding to intradermal testing. Prick testing is performed at marked sites on the inner volar aspect of the forearm. Testing for controls and each reagent is performed singly.

Reagents and controls for prick and intradermal tests include:

1. Controls:
 - a.) Negative Control: Sodium chloride solution without preservative

* e.g., patients presenting with secondary syphilis

- b.) Positive Control: Histamine:
 - i. Prick testing: histamine base 1 mg/ml
 - ii. Intradermal testing: histamine base 0.1 mg/ml
2. Reagents:
 - a.) PRE-PEN® (major determinant)
 - b.) Penicillin G 10,000 U/ml (minor determinant)

Intradermal testing will not be performed if there is a positive or uninterpretable reaction to PRE-PEN® and/or Penicillin G during the prick test. If the prick skin test results are negative the participant is qualified for intradermal testing. Study staff will perform duplicate intradermal skin testing of each reagent and single intradermal skin testing of the positive and negative controls on the inner volar aspect of the forearm. The same arm will be used for both prick and intradermal testing.

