8.2 Sample Size Considerations

The sample size for this study was selected to have adequate study power to conclude a high NPV of the PCN (B-lactam) allergy history screening questionnaire in ruling out the presence of true PCN (B-lactam) allergy. To address the objective properly, we applied Steinberg's et al.³² approach to obtain the minimal sample size needed to achieve a lower 95% confidence bound for NPV that exceeds the NPV with a useless test at a fixed level of significance with a given study power. Based on this approach, the sample size calculation depends on the prevalence of PCN allergy in the population and among observed study participants and the sensitivity and specificity of the PCN allergy diagnostic kit (PRE-PEN®). To target at least 85% power at 5% of significant level, the listed sample sizes (see table) provide lower 95% confidence bounds for NPV under the following various assumptions:

- The true population prevalence with PCN allergy: 1%, 3%, 5%
- The observed % of PCN allergy in this study: 1%, 3%, 5%
- The PCN allergy diagnostic kit with sensitivity at least 85% and specificity 95%
- 5% of participants who report a PCN allergy history will have a high-risk allergy history and therefore will not proceed to skin testing.

Population prevalence of PCN allergy	Observed % of PCN allergy in study	Estimated NPV	The lower 95% confidence bound for NPV						
			99.0%	98.4%	97.9%	97.5%	97.3%	97.0%	95.0%
1%	1%	99.84%	1259	796	635	556	526	488	351
	3%	99.51%	420	265	212	185	175	163	117
	5%	99.18%	252	159	127	111	105	98	70
3%	1%	99.84%	8119	2964	1958	1559	1421	1259	759
	3%	99.51%	2707	988	653	520	474	420	253
	5%	99.18%	1624	593	392	312	284	252	152
5%	1%	99.84%	113000	9519	4770	3378	2950	2483	1259
	3%	99.51%	37547	3174	1590	1126	984	828	420

	5%	99.18%	22533	1905	954	676	590	497	252
--	----	--------	-------	------	-----	-----	-----	-----	-----

For example, with 3% PCN allergy prevalence in population and among observed study participants, the NPV for a useless test is 97%. A useful PCN (B-lactam) allergy history screening questionnaire should have the lower 95% confidence bound for NPV greater than 97%. Based on the list a minimum sample size of 988 subjects who reported to have PCN allergy history would provide an estimated NPV = 99.51% with 85% power to conclude that the NPV of the study allergy history screening questionnaire is least 98.4% at 5% significant level.

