4.4 Treated Population

This population includes all enrolled participants who received Method 1 PST or Method 2 DOC. This analysis population will mainly be used for analyzing participants' baseline characteristics, primary outcome measures and secondary outcome measures.

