7.3 Analysis of Primary Objective

The primary analysis will be performed on the Treated population and Per Protocol population. Estimates with corresponding exact (Clopper-Pearson) 95% confidence intervals for the following measures will be provided:

- The prevalence of PCN reactivity validated either by skin test or by direct oral challenge among those participants who report a history of PCN (B lactam) allergy and who have low-risk histories.
- The NPV on true PCN (B-lactam) allergy of the algorithm / PCN (B-lactam) allergy history screening questionnaire performance in the Treated population.

The NPV for each low-risk allergy item listed on the questionnaire will be estimated and will be compared with the prevalence of PCN reactivity using exact test of binomial proportion. The p-values will be adjusted with Benjamini-Hochberg procedure.

To construct a short standardized post-study questionnaire (4-6 questions) from the PCN (B-lactam) allergy history screening questionnaire, we will first use the item-characteristic curve from Item Response Theory (IRT) to evaluate each question item's discrimination ability of true PCN (B-lactam) allergy and use variable importance evaluation functions to indicate which questions are most useful for predicting the true PCN (B-lactam) allergy. Based on the results of IRT and variable importance analyses, we will then apply machine learning approaches such as random forest (Svetnik et al., 2003) via R package caret, to select a short post-study questionnaire that has the highest NPV among those possible short questionnaires with 4-6 selected questions.

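### Only low-risk subjects are tested, so the primary NPV is one minus the low-risk reaction rate, and the 97% "useless test" mark in Protocol 8.2 rests on a prevalence the trial cannot check

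*SAP*

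**What the plan says.** SAP 3.1 names as the first primary outcome the performance of the questionnaire, "specifically the negative predictive value (NPV) of the algorithm on true PCN (B-lactam) allergy".

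Both validation methods are confined to low-risk histories. SAP Section 1 describes the PST method as "skin testing of subjects with low-risk history followed by one-step oral challenge of subjects with negative skin tests", and the DOC method has the same restriction. Protocol 6.2 states: "Participants with a higher risk of PCN allergy will not proceed to the PCN skin test or oral challenge". Protocol 6.1.2.2 adds: "Subjects who meet the higher-risk classification will be advised that further elucidation of their allergy status will require a formal allergy evaluation". Neither document plans to collect the result of that evaluation.

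The Treated population in SAP 4.4 is defined thus: "This population includes all enrolled participants who received Method 1 PST or Method 2 DOC". SAP 7.3 then plans two primary estimates with Clopper-Pearson intervals. One is the prevalence of reactivity among low-risk reporters. The other is this: "The NPV on true PCN (B-lactam) allergy of the algorithm / PCN (B-lactam) allergy history screening questionnaire performance in the Treated population".

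The sample size in Protocol 8.2 compares the NPV with that of a useless test, which is 97% in the worked example at 3% prevalence: "A useful PCN (B-lactam) allergy history screening questionnaire should have the lower 95% confidence bound for NPV greater than 97" per cent. Protocol 8.2 and SAP Section 6 both power the study to conclude that the NPV is at least 98.4%.

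For the short form, SAP 7.3 uses item response theory and machine learning "to select a short post-study questionnaire that has the highest NPV among those possible short questionnaires with 4-6 selected questions".

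**The concern.** An NPV tells a reader something about a questionnaire only when set beside the allergy rate among everyone who could have been given it. If that rate is low, a questionnaire that sorts people at random also has a high NPV. This trial collects no reference result on questionnaire-positive subjects, so the comparison rate must be assumed. A lower bound above 97% could then be read as evidence that the questionnaire works when it shows only that allergy is uncommon.

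The short form has a related limit. Every subject with a reference result has already been screened negative on the higher-risk items, so those items do not vary in the selection data and cannot show predictive value. The chosen 4-6 questions would carry an NPV that holds only after the full higher-risk list is negative, while the stated purpose is a standalone instrument for STD settings.

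**Working it through.** **Inputs.** From Protocol 8.2 and SAP Section 6: prevalence 3% (population and observed), sensitivity 85% and specificity 95% (stated for the skin-test kit), higher-risk share 5%, power 85%, alpha 5%, target bound 98.4%, stated N 988. From Protocol 2.1: skin-test reactivity 17% (anaphylaxis history), 12% (urticaria history) and 7.1% (all allergy reporters) in the earlier STD-clinic series.

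**1. The plan's own figures.**
- NPV = 0.95×0.97 / (0.95×0.97 + 0.15×0.03) = 99.51%, as stated.
- n = (z_a + z_b)² × [se/((1−se)p) + (1−sp)/(sp(1−p))] / d², where d = log((1−se)/sp) − [logit(1−0.984) − logit(p)].
- With one-sided alpha: (1.645 + 1.036)² = 7.189; bracket = 188.94; d = −1.8458 − (−4.1190 + 3.4761) = −1.2029, so d² = 1.4469.
- n = 7.189 × 188.94 / 1.4469 = 938.8. Dividing by 0.95 for the higher-risk share gives 988.2, against the stated 988. Two-sided alpha would give 1,234.

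The arithmetic holds under a one-sided 5% level. The formula uses 85% and 95% as the questionnaire's accuracy, which the trial cannot estimate.

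**2. The identity.** With N tested, all low-risk, and x reactors, prevalence is x/N and NPV is 1 − x/N, with mirrored exact intervals. For x = 9 and N = 938, prevalence is 0.96% (0.44 to 1.81%) and NPV is 99.04% (98.19 to 99.56%). The two can differ only if their reference outcomes differ. Read literally, the prevalence outcome (skin test or direct challenge) omits reactors to the one-step challenge after a negative skin test.

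**3. What passing 97% shows.** Take a questionnaire with no discrimination, so that low- and higher-risk reporters have the same allergy rate. At n = 939, using the two-sided 95% Clopper-Pearson lower bound:

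| Bound to exceed | Most reactors allowed | Pass probability at true prevalence 1% | 1.5% | 3% |
|---|---|---|---|---|
| 97% | 17 | 99.2% | 82% | 1.5% |
| 98.4% | 7 | 28% | 2.9% | about 0 |

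**4. Are the planning inputs compatible?** Overall prevalence = 0.95 × low-risk rate + 0.05 × q, where q is the allergy rate in the untested group. With 3% overall and a low-risk rate of 1 − 0.9951 = 0.49%, q = (0.03 − 0.95×0.0049)/0.05 = 51%. The assumed 85%/95% accuracy actually implies a questionnaire-positive share of 0.85×0.03 + 0.05×0.97 = 7.4% rather than 5%. Even on that share, q = 0.0255/0.074 = 34%. Both exceed the 12% and 17% subgroup rates. Conversely, with 3% overall, 5% higher-risk and q at 12% or 17%, the NPV is 97.5% or 97.7% and the sensitivity 0.05q/0.03 is 20% or 28%.

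**5. The benchmark over q**, holding the low-risk rate at 0.49%:

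| q in the untested 5% | Useless-test NPV |
|---|---|
| 0% | 99.53% |
| 12% | 98.93% |
| 17% | 98.68% |
| about 51% | 97% |
| 100% | 94.53% |

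**The case against.** The case on the other side has real force.

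- **No formal success rule.** The 97% sentence is a worked example in Protocol 8.2. SAP Section 6 does not repeat it, and SAP 7.3 plans estimates with exact intervals and no overall test. A reader might infer that the trial has a success rule that would certify a useless questionnaire. The documents do not go that far.
- **Matched scenarios behave well.** The useless-test value at 1% prevalence is 99%, not 97%. A lower bound above 99% at n = 939 allows at most 3 reactors, and a questionnaire with no discrimination then passes 1.6% of the time. The 99.2% figure arises only when true prevalence is 1% and the mark stays at 97%. It measures the cost of misjudging prevalence.
- **A fixed target exists.** Both documents power the study for 98.4%.
- **Some discrimination is assessed.** SAP 7.3 compares each low-risk item's NPV with the prevalence of reactivity, with Benjamini-Hochberg adjustment. It would be wrong to say discrimination is not studied at all. What is missing is discrimination between low- and higher-risk reporters.
- **Restricting testing is deliberate.** Appendix B of the protocol marks testing as contraindicated after a higher-risk history. An NPV estimated in low-risk reporters is a valid estimate of that quantity.
- **Limits of the comparison rates.** The 12% and 17% are skin-test rates from one older series, and 7.1% there refers to all reporters, so it cannot serve as a higher-risk rate. The 0.49% is a planning value, not an observation.

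All of these points stand, and they narrow the concern. They do not supply the missing quantity: no data in the trial can establish the prevalence behind 97%, and the higher-risk items remain constant in the short-form selection.

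**Conclusion.** The point holds as one about what the primary result can mean. Given a single reference outcome, the two primary outcomes are one number. The 97% mark separates a useful from a useless questionnaire only if prevalence among all reporters is close to the assumed 3%. A questionnaire with no discrimination between low- and higher-risk reporters passes it with probability 1.5% at 3%, 82% at 1.5% and 99% at 1%. Prevalence of 1% is one of the plan's own scenarios. The inputs behind 3% and 99.51% require about 51% allergy in the 5% who are not tested, well above the rates the protocol cites.

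These figures assume 939 tested subjects, a two-sided exact bound, and equal allergy rates in the two risk groups for the no-discrimination case. The 51% also assumes the plan's 5% higher-risk share.

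A reader might conclude that the NPV estimate is invalid or that higher-risk subjects ought to have been tested. Neither follows. The planned estimate and interval are sound for low-risk reporters; the correction concerns the claim attached to them.

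**What to change.** In SAP 7.3:

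1. Define one reference outcome: a positive skin test or a reaction to any oral challenge, including the one-step challenge after a negative skin test.
2. Report one parameter, NPV = 1 − reactivity in low-risk reporters, with its exact interval.
3. Judge the lower bound against the 98.4% already in SAP Section 6, and drop the 97% reading of a useful questionnaire. At n = 939 a two-sided exact bound above 98.4% allows 7 reactors and is met with probability 90.5% if low-risk reactivity is 0.49%, so this does not itself require a larger sample.
4. State that sensitivity, and discrimination between low- and higher-risk reporters, are not estimated.
5. Add a sensitivity table that rebuilds the useless-test benchmark from the observed low-risk rate and higher-risk share, with the allergy rate in the untested group running from 0 to 100% and 12% and 17% marked.
6. State that the short questionnaire's NPV applies only to people already negative on the full higher-risk list.

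The cost is SAP wording, one extra table and a narrower claim. No additional testing is involved.

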3.2 Secondary Outcome measures

- Acceptability
 - Proportion of study subjects who find the testing procedures to be helpful.
 - Reasons why study subjects refuse to participate in the study.
 - Proportion of study subjects who were negative on oral challenge who now feel confident in taking PCN or similar antibiotics.
 - Proportion of study providers who will not offer PCN allergy assessment in the future.
- Feasibility
 - Proportion of study providers who will offer PCN allergy assessment in the future.
 - Reasons why study providers will not offer PCN allergy assessment in the future.
- Both acceptability and feasibility
 - Types and frequencies of elicited reactivity to PCN through skin testing and oral challenge among study subjects.

4. Analysis Populations

This analysis plan describes six different analysis populations that are used for different purposes. The final statistical report will include an accounting of all eligible persons screened and the number enrolled. The reason for excluding any data from any analysis population will be documented.

